## **Objectives**

This study aims to compare two groups of healthy (non-lactose intolerant) subjects who are irregular milk consumers, due to milk induced gastrointestinal disorders, with another group of healthy subjects who consume milk regularly, without symptoms, in relation to the primary and secondary objectives here described.

By performing a milk test in which volunteers ingest 250 ml of UHT semi-skimmed milk, primary objectives include the evaluation of:

- plasmatic response of milk-derived peptides;
- plasmatic profile of GI hormones;
- plasmatic profile of endocannabinoids and N-acyl-ethanolamines.
- urinary profile of lactose over 24 h;

Secondary objectives include the assessment of:

- baseline and postprandial plasma profile of aminoacids;
- baseline and postprandial blood glucose;
- baseline and postprandial GI symptoms;
- baseline serum concentration of dipeptidyl peptidase IV (DPPIV);
- baseline and postprandial serum activity of dipeptidyl peptidase IV (DPPIV);
- urinary excretion of indican as marker of protein digestibility;
- correlations of GI symptoms with appetite ratings and blood glucose, plasma GI hormones, plasma peptides and amino acids as well as with urinary excretion of lactose and galactose + glucose;
- the composition of the intestinal microbiota (metagenomic analysis);
- the psychological profile through questionnaires on the perception of quality of life, on levels of depression, anxiety and stress and on eating behavior.

Further secondary objectives include the assessment of:

- the prevalence of lactose malabsorption in the two groups, by using results from Lactose H2 breath test performed during the recruitment procedure;
- urinary excretion of lactulose, mannitol and sucralose as markers of intestinal permeability after an oral challenge of these 3 sugar probes.

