Anthropometric data of weight and height will be measured as well.

Fecal samples, stored at -40°C, will be used for DNA extraction according to the standard operating procedures of the International Human Microbiome Consortium (<http://www.human-microbiome.org/>). Statistical analysis will be carried out by the most appropriate methods in order to infer the associations between specific microbiota signatures and clinical, dietary and metabolomic variables.

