## Statistical analysis plan

### Sample size calculation

The sample size for this study has been calculated on the basis of the primary endpoints here listed:

- milk-derived peptides plasma concentrations after milk consumption;
- lactose urinary excretion after milk consumption;
- post-prandial plasma profile of GI hormones and ECs.

Considering circulating mean values and standard deviations reported by Deth et al. (2016) in blood of healthy population, power analysis indicated that a sample size of 19 participants per group is sufficient to detect a minimum variation of 40% in circulating BCM-7 with a power of 80% and an  $\alpha = 0.05$ .

Considering excreted % of lactose in urine, hydrogen concentration in breath and relative standard deviations as reported by Bezerra et al. (1990) a sample size of 19 participants per group is sufficient to detect a 15% minimum variation of lactose and a 50% minimum variation of hydrogen in healthy subjects, with a power of 80% and an  $\alpha = 0.05$ .

Regarding post-prandial plasma profile of GI hormones and ECs, our previous studies showed that a sample size of 13 participants is adequate to find significant differences with an 80% power and an  $\alpha = 0.05$ . (Mennella et al., 2015; Mennella et al., 2016).

The participant number will be increased up to 40 (20 subjects per group) in view of possible dropouts.

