### Statistical analysis

Data will be expressed as means  $\pm$  SEMs, unless otherwise specified.

Two-tailed P values lower than 0.05 were considered significantly different

Missing data will be handled as such, i.e., no imputation of missing data will be performed.

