### *Continuous variables with repeated measures*

Normality of measures, for each time, will be assessed using the Shapiro-Wilk test.

Differences of variables between baseline and over time within and between the groups, for normally distributed variables, will be tested by ANOVA with repeated measures on one factor (time) and Bonferroni adjustment for multiple comparisons. For non-normally distributed variables, Friedman test and pairwise Wilcoxon as a *post hoc* test will be applied.

Analysis of quartiles will be performed for both baseline values and pairwise time points ( $\Delta$ ) upon milk ingestion.

For these variables with repeated measures, the total area under the curves (AUCs) will be also estimated using the linear trapezoidal rule, and differences in AUCs between the groups will be assessed by proper parametric or non-parametric analyses including as covariates the potential confounding variables measured at baseline.

Pearson's correlation coefficients will be calculated to assess bivariate associations among continuous variables at baseline or partial associations of estimated AUCs controlling for baseline values for variables with repeated measures.

Spearman's rank correlation will be used to assess association between non-parametric variables collected and microbiota related variables (e. g. species abundance and genes abundance).

In order to explore differences in microbiome profiles, a Partial Least Squares Discriminant Analysis was applied.

Furthermore, principal component analyses (PCA) on specific variables at baseline or unstandardised residuals correlation between AUCs and related baseline values will be also performed in order to extract features relevant to the cluster structure. Moreover, statistical significance of the distance between groups in the PCA analysis will be computed using the Hotelling T2 test.

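### No multiplicity control is specified for the Spearman correlations with species and gene abundances, so about 5% of the tests would be chance findings if no true association exists

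*Combined protocol and SAP*

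**What the plan says.** Under Continuous variables with repeated measures, the SAP plans that Spearman's "rank correlation will be used to assess association between non-parametric variables collected and microbiota related variables", giving as examples "species abundance and genes abundance". It states no number of features, no abundance or prevalence filter, no family of tests, no pre-specified subset and no exploratory label.

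The general rule under Statistical analysis is "Two-tailed P values lower than 0.05 were considered significantly different". The one multiplicity adjustment in the documents belongs to a different analysis: "ANOVA with repeated measures on one factor (time) and Bonferroni adjustment for multiple comparisons".

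The purpose of the microbiota work is given at the end of the Milk test section, where the method is left open: "Statistical analysis will be carried out by the most appropriate methods in order to infer the associations between specific microbiota signatures". The signatures are to be related to the trial's clinical, dietary and metabolomic data. The Objectives list microbiota composition as a secondary objective. Further analyses allows every analysis to be repeated in lactose-tolerant and lactose-malabsorber subgroups.

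**The concern.** Metagenomic data give many features per subject, and the trial measures many other variables. Crossing the two produces a large grid of correlations. The plan gives no rule for that grid beyond the general 0.05 threshold, so a fixed fraction of the grid is expected to pass by chance. The plan sets an adjustment for the repeated-measures ANOVA and none here.

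What is at stake is the interpretation of any reported microbiota signature. If the error control is chosen, or left out, after the P values are seen, the results do not show how many of the listed associations chance alone would produce. Ranking the primary endpoints would not help, because this screen lies outside them.

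**Working it through.** **Inputs from the documents**
- Threshold: two-tailed 0.05 (Statistical analysis).
- Subjects: 2 × 20 = 40 (Sample size calculation).
- Number of microbiota features: not stated.
- Number of other variables: not stated. A minimum list of single measures can be counted from the Milk test and Gut permeability test sections: 7 hormones, 1 glucose, 2 DPPIV measures, 3 urinary analytes (lactose, galactose + glucose, indican) and 2 permeability markers. That is 7 + 1 + 2 + 3 + 2 = 15, before amino acids, peptides, endocannabinoids, symptoms and questionnaires. How many would be treated as non-parametric is unknown, because the SAP tries transformation first.

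The plan gives no count of tests or expected false positives, so there is no figure of its own to reproduce.

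**Expected chance findings.** With m = features × variables and no true association, the expected number of results with P < 0.05 is 0.05 × m. The feature and variable counts below are assumptions.

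| Features | Variables | m | Expected by chance |
|---|---|---|---|
| 50 | 1 | 50 | 2.5 |
| 100 | 1 | 100 | 5 |
| 100 | 10 | 1,000 | 50 |
| 200 | 20 | 4,000 | 200 |
| 300 | 30 | 9,000 | 450 |
| 5,000 (genes) | 20 | 100,000 | 5,000 |

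If all 15 counted variables entered the screen, 14 features would give 0.05 × 14 × 15 = 10.5 and 134 features would give 0.05 × 134 × 15 = 100.5. For independent tests, the chance of at least one false positive is 1 − 0.95^m, already 0.92 at m = 50.

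**Does sample size matter?** Null Spearman correlations were simulated for 200 features × 20 variables. The mean number with P < 0.05 was 203 at n = 20, 202 at n = 40 and 200 at n = 400. The count does not depend on n.

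**Does correlation among features matter?** At n = 40, with a shared factor giving correlation 0.3 among the features and among the variables, the mean was 198. The 95% range widened from 176–227 to 111–370. Dependence changes the spread, not the expectation.

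**How large a chance correlation looks.** The critical |rho| is t / √(n − 2 + t²). With n = 40, t(38) = 2.024, so |rho| = 2.024 / √(38 + 4.10) = 0.312.

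**Effect of adjustment.** In the same null simulations (several grid sizes, n from 20 to 400), Benjamini-Hochberg at 5% over the whole grid gave any discovery in about 5–9% of studies. Bonferroni shows the upper end of the cost, since Benjamini-Hochberg rejects everything Bonferroni rejects at the same level. At n = 40, power for a true rho of 0.5 was taken as 1 − Φ(z − atanh(rho) × √((n − 3)/1.06)), with z the two-sided critical value:

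| m | Critical abs. rho (Bonferroni) | Power at rho = 0.5 |
|---|---|---|
| unadjusted | 0.31 | 90% |
| 200 | 0.55 | 34% |
| 2,000 | 0.61 | 17% |
| 4,000 | 0.63 | 13% |

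**The case against.** The documents nowhere say that these P values will go unadjusted. That is read from silence: one general threshold and no adjustment attached to the Spearman sentence. The Milk test section's open wording on methods does not exclude false-discovery control. This is fair, and the accurate statement is that no control is specified. But open wording names no error rate and leaves the choice until after the data are seen.

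Microbiota associations also have modest standing. The Objectives name composition only, and their separate correlation objective covers symptoms against appetite, glucose, hormones, peptides, amino acids and urinary sugars. The association aim rests on the Milk test section alone. This stands and limits the weight of the point.

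A reader might go further and infer that the results will contain tens to hundreds of chance associations because only 40 subjects are studied. The documents do not support that. They give no feature count, the expected number could be below ten or in the thousands, it assumes no true association, and it does not depend on sample size. Nor can one say that most reported signatures will be noise, since that depends on the unknown share of true associations. If the full set of P values were published, a reader could apply an adjustment; the plan promises neither full nor selective reporting.

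**Conclusion.** The point holds as a gap in a secondary analysis. The SAP specifies no multiplicity control for the microbiota correlations, and applying its general threshold gives an expected 0.05 × m chance findings if nothing is associated. Since m is not stated, the size is a range: 50 to 450 for an assumed 1,000 to 9,000 tests, fewer if few variables enter, and thousands at gene level. The sample size enters in two other ways: at n = 40 every nominal finding has |rho| of at least 0.31 and so looks substantial, and power is limited once an adjustment is applied. The primary comparisons and the sample size justification are not affected. The change should be made, but it is not critical to the trial's main conclusions.

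**What to change.** Keep Spearman's correlation and add to the SAP, before any microbiota correlation is run:

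- two families of tests, species and genes, each taken across all the non-microbiota variables tested and including any repeats in the lactose-tolerant and malabsorber subgroups;
- Benjamini-Hochberg control of the false discovery rate within each family, with a single q threshold fixed in advance, for example q < 0.05;
- a prevalence filter for features, with its cut-off set before any correlation is computed;
- reporting of q values and of the number of tests in each family;
- a statement that associations reaching only nominal P < 0.05 are exploratory.

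This costs a few sentences in the SAP and a standard function call in R, with no new data. The downside is that some nominally significant associations will no longer be called findings, and power for individual associations falls. The Bonferroni figures above show the upper end of that loss.

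### The exploratory PLS-DA of the microbiome has no stated validation; if features greatly outnumber the 40 subjects, it will separate the groups almost perfectly on noise alone

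*Combined protocol and SAP*

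**What the plan says.** The composition of the gut microbiota is a secondary objective: "the composition of the intestinal microbiota (metagenomic analysis") (Objectives). The multivariate group comparison gets one sentence in the SAP section Continuous variables with repeated measures, which says that, as an exploration of profile differences, "a Partial Least Squares Discriminant Analysis was applied". That sentence gives no number of components, scaling, feature filter, cross-validation, permutation test, hold-out set or performance measure.

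No other section fills the gap:

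- The text on fecal samples in the Milk test section is generic: "Statistical analysis will be carried out by the most appropriate methods in order to infer the associations between specific microbiota signatures".
- Further analyses names R as the software and nothing more on this point.
- The Bonferroni adjustment belongs to the repeated-measures ANOVA.
- The one multivariate significance test belongs to the PCA: "statistical significance of the distance between groups in the PCA analysis will be computed using the Hotelling T2 test".

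The kind of feature is indicated in the sentence on Spearman correlation, which mentions "species abundance and genes abundance". The number of features is not given. On numbers of subjects: "The participant number will be increased up to 40 (20 subjects per group) in view of possible dropouts".

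**The concern.** PCA does not see the group labels; PLS-DA does, and it chooses directions because they separate the labelled groups. When there are many more features than subjects, such directions exist by chance. A score plot with two clean clusters, or a list of the most influential taxa, then looks the same whether or not habitual and non-habitual milk consumers differ.

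The plan attaches a formal test to the unsupervised method and none to the supervised one, which needs it more. PLS-DA is also the only method named explicitly for group differences in the overall microbiome profile. At stake is whether that comparison can return a negative answer.

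**Working it through.** **Inputs.** From the documents: 20 + 20 = 40 subjects, and microbiome features of the species- and gene-abundance kind. Assumed, because the documents are silent: the number of features p (10 to 5000), the number of components (1 to 3), autoscaling, and the correlation between features. The plan states no performance figure for PLS-DA, so there is none to reproduce.

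**Step 1: why separation on noise is expected.** After centring, 40 subjects span at most 40 - 1 = 39 dimensions. With 39 or more linearly independent features, some linear combination reproduces any labelling exactly. PLS-DA with few components need not reach that combination, so the question is how close it comes.

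For one component the weights are proportional to X'y, with y = +1 or -1. The score of subject i is then proportional to

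y_i |x_i|² + Σ_{k≠i} y_k (x_i'x_k).

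The first term is the subject's own label fed back, of size about p. The second is noise with standard deviation about √(39p). Hence, for independent noise features,

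apparent accuracy ≈ Φ(p / √(39p)) = Φ(√(p/39)).

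For p = 50, √(50/39) = 1.13 and Φ = 0.87. For p = 100, √(100/39) = 1.60 and Φ = 0.95.

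**Step 2: simulation.** Independent Gaussian noise unrelated to group, 20 versus 20, autoscaled PLS-DA, 100 data sets per setting, accuracy on the data used for fitting:

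| Features p | Φ(√(p/39)) | 1 component | 2 components | 3 components |
|---|---|---|---|---|
| 10 | 0.69 | 0.69 | 0.71 | 0.72 |
| 20 | 0.76 | 0.77 | 0.82 | 0.84 |
| 50 | 0.87 | 0.87 | 0.96 | 0.99 |
| 100 | 0.95 | 0.95 | 0.998 | 1.00 |
| 200 | 0.99 | 0.99 | 1.00 | 1.00 |
| 500 | 1.00 | 1.00 | 1.00 | 1.00 |

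The hand formula and the one-component column agree.

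**Step 3: features more like microbiome data (two components).**

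- Zero-inflated relative abundances: 0.92 (p = 50), 0.975 (100), 0.996 (200), 0.999 or more (500 and above).
- The same after centred log-ratio transformation: 0.95, 0.996, 1.00, 1.00.
- Correlated noise, p = 500: 1.00 with 30% shared variance, 0.96-0.97 with 60%, 0.84-0.86 with 80%. With three components all of these are 0.98-1.00.

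**Step 4: the same noise, validated.** Stratified five-fold cross-validation, with scaling inside the folds, gives 0.48-0.52 on the independent and abundance-type noise. It was not run on the correlated noise.

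A label-permutation test of cross-validated accuracy (500 features, two components, 99 permutations) rejected in 3% of 200 noise data sets, that is 6. At a nominal 5% the standard error is √(0.05 × 0.95 / 200) = 0.015, so 3% lies (0.05 - 0.03)/0.015 ≈ 1.3 standard errors below nominal and is compatible with it.

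**Step 5: can the PCA's test be borrowed?** No. Hotelling's T² applied to the PLS scores gave p < 0.05 in 100% of noise data sets with 50 or more features, because the scores were chosen to separate the groups.

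**The case against.** The strongest reply is that the plan is silent rather than wrong. The PLS-DA is meant to explore, no significance claim or decision rule is attached to it, and nothing says that fitted accuracy will be reported or treated as proof. The analysts may well validate as a matter of course. All of this is fair and limits the weight of the point. It does not remove it: a separation plot is the natural output of this method, nothing commits anyone to validate it, and an exploratory analysis must still be able to show no difference.

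A second reply is that the effect depends on figures the documents do not give. This also stands. With 10 to 20 features, apparent accuracy on noise is 0.69-0.84 across one to three components. With 500 very strongly correlated features and two components it is 0.84-0.86. The sentence mentioning species and gene abundances concerns Spearman correlation, and nothing says that both sets enter the PLS-DA. Yet even the mild cases lie well above 0.50, so validation is needed throughout the range.

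A reader might infer that the whole microbiota objective would yield no evidence. The documents do not support that. One fecal sample per subject makes each taxon a continuous variable without repeated measures. The section of that name gives such variables a t test or Mann-Whitney test, with ANCOVA or Quade's test for covariates. Those tests are untouched by this point.

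**Conclusion.** The point holds as a recommended change of moderate weight. No validation step for the PLS-DA appears anywhere in the documents. If features greatly outnumber the 40 subjects (about 100 or more with two components, or about 50 with three), apparent separation of the groups is close to complete on independent noise and says nothing about a true difference. Feature counts of that order are plausible for species or gene abundances, but they are an assumption, as is the number of components.

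It would be too strong to say that PLS-DA on 40 subjects always separates the groups. The cause is the ratio of features to subjects, and the effect is weaker with short taxon lists or very strong correlation. Microbiota composition is a secondary objective, the analysis is labelled exploratory, and no primary endpoint or sample-size figure depends on it.

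**What to change.** In the SAP section Continuous variables with repeated measures, add to the PLS-DA sentence that:

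1. The result will be judged on repeated cross-validated error, with choice of component number, scaling and any feature selection carried out inside the folds.
2. A label-permutation p value will be reported for that cross-validated performance, with the number of permutations stated in advance.
3. Score plots and variable-importance lists will not be presented as evidence of a group difference unless the permutation test supports one.

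The feature set entering the model should be named at the same time. PERMANOVA on a stated distance would be a reasonable addition, but it is optional.

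The cost is a few sentences and some computing time in R, with no new data or subjects. The downside for the authors is a result that may look less striking.

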## **Further analyses**

Since the prevalence for lactose malabsorption over the enrollment will be assessed, all the statistical analyses reported above may be applied to subgroups of subjects classified as "lactose tolerants (LT)" and "lactose malabsorbers (LM)" in order to check differences between the two groups and/or correlations between variables assessed.

Chi-means will allow to assess differences between subgroups classified on the basis of lactose absorption capacity of subjects as detected by lactose H2 breath test.

Statistical analyses and data visualization will be carried out in R environment (<http://www.r-project.org>).
